3. ETHICAL CONSIDERATIONS

Ethical approval to conduct the study was obtained from the University Research Ethics Committee (UREC) at the University of East London and from the Health Research Authority (HRA) and will be conducted with Central and North West London (CNWL) NHS trust. Potential risks associated with tDCS are minor discomfort from wearing the tDCS electrode net and minor itchiness that immediately cease after stimulation, this is explained to the participants prior to starting. Participants will be reminded that they could stop the experiment at any time they wish, if they felt too much discomfort or distress.

4. DATA PROTECTION

All data will be anonymised, treated confidentially and retained in accordance with the Data Protection Act, stored for a limited period of time on password protected hard drives. Each participant will be given a participant number that can be de-coded by the researcher. Hard copies of questionnaires and consent forms will be stored in a locked filing cabinet in a lockable room then destroyed in accordance with the university's data protection policies.

5. STATISTICAL ANALYSIS PLAN

Data source

Behavioural data sets will be obtained from computer-based cognitive tasks and questionnaires that participants complete during the stimulation sessions. The results obtained from completing these tasks and questionnaires generate measures for addiction-related symptoms such as cravings, impulsivity, risk-taking behaviour, delay aversion and control inhibition. Each participant will produce data at two time points for G-SAS and CGT measures and at eight time points for VAS, PG-BOCS and secondary measures. Electroencephalography (EEG) resting state neural oscillatory activity will be recorded for 5 minutes prior and 5 minutes after the tDCS intervention.

Analysis objectives

The investigators will study whether the behavioural and cognitive data obtained from participants in different time points are significantly different between the two treatment groups. In addition, the investigators will investigate if electrophysiological measures (EEG resting state) predict behavioural outcomes obtained from the cognitive task performance during tDCS experiments, as well as studying the task performance progression comparing every week's results to the baseline.

Analysis sets/Subgroups

The following data sets subgroups will be analysed:

1. Experimental - Stimulation with CBT: Participants that attend to 8 weekly sessions of tDCS stimulation and that following the tDCS session, they attend to a cognitive behavioural therapy (CBT) session.
2. Sham Comparator - Sham with CBT: Participants that attend to 8 weekly sessions of sham tDCS and that following the tDCS session, they attend to a CBT session.

The aim is to study whether the combination of stimulation and therapy help to improve the treatment outcomes in comparison with CBT alone.

Variables and covariates

Primary Dependent Variables:

1. Pathological Gambling adapted Yale-Brown Obsessive Compulsive Scale (PG-YBOCS) scores for gambling severity.
2. Visual Analog Scale (VAS) scores for gambling cravings.
3. Gambling Severity Symptoms Assessment (G-SAS) for gambling symptoms.
4. Cambridge Gambling Task's (CGT) scores for gambling behaviour.

Secondary Dependent Variables:

1. Stop signal task's (SST) scores for inhibition control.
2. Information Sampling Task's (IST) scores for impulsivity.
3. EEG resting state oscillatory neural activity.

Independent Variables:

1. tDCS condition (Stimulation or Sham)
2. Time (sessions 1 to 8)

Covariates:

1. Age
2. Gender

Handling of missing values

We expect to have very few cases of missing values due to the methodology used in the study. The variables will be measured with a computer software that doesn't allow to continue with the test unless one of the options is selected. The only possible missing values would come by an error on the whole task, which will result in no data at all. In this case, we would withdraw this participant from the analysis of that specific task.

The possible missing values that we would expect to deal with, will come from the covariates measures that are obtained from paper-based questionnaires. The researcher checks before the participant leaves the session that they have completed all the questions. However, if we have to deal with missing values, we will use common-point imputation that is commonly used for rating scales, which is the case in our questionnaires. With this technique we would use the most commonly chosen value for the rest of the questions and substitute it for the missing value

Statistical Procedures

The analysis performed will be as in Loo et al (2012): the two treatment groups will be analysed for differences in demographic and clinical variables at baseline using χ^2 -tests for categorical variables

and t-tests for continuous variables. To test the effect of tDCS on test performance, a 2 x 2 mixed between-within ANOVA will be conducted. The between-groups factor will be stimulation condition (real stimulation vs sham) and the within-participants factor will be time (change from baseline). Analyses will test for main effects of stimulation condition and session as well as the stimulation-session interaction.

Secondary measures involve cognitive tasks and EEG resting state neural oscillations recording. Differences between sessions scores will be analysed with mixed between-within repeated measures ANOVA. The between-groups factor will be tDCS condition (real tDCS vs sham tDCS) and the within-participants factor will be time (change from baseline). Analysis will test for main effects of group (tDCS condition) as well as for tDCS-time interaction to investigate the presumable accumulative effects of tDCS. This analysis will serve to study if specific EEG resting state oscillatory activity correlates with the modulatory effect of tDCS on task performance and to explore the presumable accumulative effect of tDCS across time.

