1. PROCEDURE

The research consists on studying the effects of tDCS in combination with cognitive behavioural therapy (CBT) in adults diagnosed with gambling disorder that attend the UK National Problem Gambling Clinic. The design of the study consists on a double blind randomized control interventional trial with parallel assignment (two interventions – tDCS in combination with CBT that will be evaluated against CBT alone).

Participants will be split in two groups depending on the treatment they receive. The treatment groups will be: tDCS real stimulation with CBT or tDCS sham with CBT. Real stimulation condition involves the application of tDCS stimulation for 20 minutes whereas sham condition is used as a control (similar to a placebo).

The investigators aim to have a total of 32 participants diagnosed with gambling disorder based on the Problem Gambling Severity Index (PGSI). There will be 16 participants per condition, having two conditions (real stimulation and sham).

Treatment 1. Participants will attend 8 weekly sessions where they receive tDCS real stimulation while complete CANTAB cognitive tasks to measure cognitive functions and following this, they will attend a CBT session.

Treatment 2. Participants will attend 8 weekly sessions where they receive sham tDCS, while complete CANTAB cognitive tasks to measure cognitive functions and following this, they will attend a CBT session.

Primary endpoint/outcomes

1. Change in scores on the Yale-Brown Obsessive Compulsive Scale adapted for Pathological Gambling (PG-YBOCS). [Time Frame: Change from baseline PG-YBOCS scores at week 2, 3, 4, 5, 6, 7 and 8].
2. Change in scores on the Visual Analogue Scale (VAS). [Time Frame: Change from baseline VAS scores at week 2, 3, 4, 5, 6, 7 and 8].
3. Change in scores on the Gambling Symptom Assessment Scale (G-SAS). [Time Frame: Change from baseline G-SAS scores at week 8].
4. Change in scores on the Cambridge Gambling Task (CGT). [Time Frame: Change from baseline CGT scores at week 8].

Secondary endpoints/outcomes

1. Change in scores on the Information Sampling Task (IST). [Time Frame: Change from baseline IST scores at week 2, 3, 4, 5, 6, 7 and 8].

2. Change in scores on the Stop Signal Task (SST). [Time Frame: Change from baseline IST scores at week 2, 3, 4, 5, 6, 7 and 8].
3. Changes in encephalography (EEG) neural oscillatory activity. [Time Frame: Correlation of tDCS and EEG activity in weeks 1, 2, 3, 4, 5, 6, 7 and 8].

Primary objective

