2. MATERIALS

Participants

The sample size will be 16 participants per group (2 groups) that attend 8 treatment sessions.

Inclusion criteria

Male or females between 18 and 65 years of age diagnosed with disordered gambling based on the Problem Gambling Severity Index (PGSI) who can speak and read English, capable of giving informed consent, and don't have any of the exclusion criteria.

Minimum Age: 18 Years

Sex: All

Gender Based: No

Accepts Healthy Volunteers: No

Exclusion criteria

- a. History or evidence of chronic or residual neurological disease.
- b. A pacemaker or deep brain stimulation.
- c. Metal implants in head or neck area (e.g. postoperative clips after intracerebral aneurysm; arterial aneurysm in the vascular system, implantation of an artificial hearing aid).
- d. Intracerebral ischemia/history of bleeding.
- e. Prior evidence of epileptic seizures, history of epilepsy.
- f. History of head injury with loss of consciousness.
- g. Any serious medical conditions (disease of the internal organs).
- h. Pregnancy or breast-feeding.
- i. Negative screening from the clinic psychiatrist

Software

This research uses a CE marked medical device, transcranial direct current stimulation (tDCS) built in the international company Neuroelectrics (<https://www.neuroelectrics.com/products/>). Specifically, Starstim® is a wireless hybrid EEG/tCS neurostimulator system. It includes the comfortable neoprene head cap where the electrodes can be easily inserted. Starstim® complies with the European legislation for clinical research.

Cognitive and physiological measurement tools

Primary outcomes:

1. Yale-Brown Obsessive Compulsive Scale adapted for Pathological Gambling (PG-YBOCS): it is a 10-item questionnaire that measures the gambling severity. The scores range from 0 to 4. The questions 1 to 5 assess urges and thoughts associated with gambling disorder, and the rest of the questions assess the behavioural component of the disorder in the past week. The total score will be calculated as well as the separate scores. Gambling severity will be higher with higher scores (we will obtain measures of PG-YBOCS in all sessions 1,2,3,4,5,6,7 and 8).

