- Masking: Double (Participant and Operator) Participants will be allocated either to a tDCS Stimulation condition or to a tDCS Sham condition.
- Allocation: Randomized

Trial setting

The trial will run at The UK National Problem Gambling Clinic (NPGC), in London. This is a single centre and it consists on an educational project and therefore a non-commercial trial.

There are not specific requirements to run the trial or different types of site. All participants will be recruited at the NPGC through members of the staff when potential participants contact the clinic to receive treatment for gambling disorder.

Patients that contact with the health care team at the NPGC will be offered the opportunity to participate voluntarily in the research. If they are interested they will need to confirm that they meet the inclusion criteria of the study which appears in the invitation letter and will be given the researcher contact details to obtain more information about the trial.

Trial procedures

The intensity for neuromodulation will remain constant across all groups at 1.8 milliamps (mA), which is a standard intensity for induced cognitive change in the tDCS literature. In the sham condition, participants will experience only 60 seconds of tDCS stimulation with 1.8 mA intensity (30 seconds ramp up and 30 seconds ramp down), which is enough to induce a tingling sensation that is associated with tDCS neuromodulation but at the same time this is not enough to alter neural activity and the left 19 minutes of the tDCS intervention they will receive 0 mA intensity. Electroencephalography (EEG) resting state oscillatory activity will be recorded during 5 minutes before and 5 minutes after tDCS.

Participants will be randomly allocated either to a real stimulation condition or to a control condition (sham). Each participant will attend to a 20 minutes transcranial direct current stimulation (tDCS) weekly session for 8 consecutive weeks (8 sessions). During the sessions they will complete cognitive tasks and questionnaires for a total time of 1 hour to assess individual characteristics (e.g. impulsivity, risk-taking behaviour) and where EEG resting state will be recorded to inform about the neurophysiology of tDCS effects in task performance.

The participant will complete:

- The consent form
- A series of questionnaires to assess cravings, addiction severity and gambling symptoms.

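### The plan does not say that all randomised participants are analysed, or how missed sessions and withdrawal are handled; followed as written, the analysis tends towards completers

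*Combined protocol and SAP*

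**What the plan says.** Section 5, Analysis sets/Subgroups, opens with "The following data sets subgroups will be analysed" and lists two entries, each with an arm label. The first is "Participants that attend to 8 weekly sessions of tDCS stimulation" and the second "Participants that attend to 8 weekly sessions of sham tDCS", both followed by CBT.

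Much the same language describes the planned schedule elsewhere. Section 1 has "Participants will attend 8 weekly sessions where they receive tDCS real stimulation", and Trial procedures in section 2 is similar. Participants in section 2 gives the target as "The sample size will be 16 participants per group (2 groups) that attend 8 treatment sessions".

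On stopping, section 3 says "Participants will be reminded that they could stop the experiment at any time they wish, if they felt too much discomfort or distress".

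Handling of missing values in section 5 has two rules. For computer-measured variables it says "The only possible missing values would come by an error on the whole task, which will result in no data at all", and it removes the person concerned from the analysis of that task. For paper questionnaires it fills an unanswered item with the respondent's most frequent answer to the other questions.

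Statistical Procedures specifies a 2 x 2 mixed ANOVA and, for secondary measures, a mixed repeated-measures ANOVA. It adds that the analysis will follow a cited study. G-SAS and CGT are taken only at sessions 1 and 8; PG-YBOCS, VAS and the secondary measures are taken at all eight.

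**The concern.** A superiority comparison of randomised arms needs its analysed population fixed in advance. Here the only text under the analysis-sets heading refers to attendance at all eight sessions, and someone who attends five has no stated place. If the text is only an arm label, the population is undefined and could be chosen after the data are seen.

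The stated reasons for expecting few missing values are software that forces a response and a check of the forms before the participant leaves. Both apply only to people who attend. Neither rule reaches a missed visit or a withdrawal.

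At stake is the balance that randomisation provides. If people leave for reasons linked to how they are doing, and this happens differently with real and sham stimulation, those who remain are no longer comparable. With 32 participants, a few losses carry weight.

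**Working it through.** **1. Is there a rule anywhere?** Reading the document through:

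| Situation | Rule in the plan |
|---|---|
| Error on a whole computer task | Person removed from that task's analysis |
| Unanswered questionnaire item | Common-point imputation |
| Missed session | None |
| Withdrawal before session 8 | None |
| All randomised, by allocated arm | Not stated |

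The plan's own sample size cannot be reproduced: no alpha, power, effect size, SD or dropout is given for 16 per group.

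**2. Whom would the ANOVAs lose?** Assume an independent miss rate m per session, session 1 always attended, and incomplete cases dropped.

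- ANOVA on sessions 1 and 8: expected number kept = 32(1 − m).
- ANOVA on all eight sessions: expected number kept = 32(1 − m)^7.

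| m (assumed) | Sessions 1 and 8 | All eight sessions |
|---|---|---|
| 2% | 31.4 | 27.8 |
| 5% | 30.4 | 22.3 |
| 10% | 28.8 | 15.3 |

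A two-time analysis keeps someone who misses session 3; an eight-session analysis does not. For G-SAS and CGT the two times must be sessions 1 and 8, so anyone who leaves before session 8 has no change score. For PG-YBOCS and VAS the plan does not say which two times the 2 x 2 ANOVA uses.

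**3. Bias when loss differs by arm.** All inputs except 16 per arm are assumed. The unit is the SD of change from baseline. The interaction F of a 2 x 2 mixed ANOVA equals the squared two-sample t on change, so a t-test among completers is the plan's test. There is no true effect and 4 of 16 are lost per arm. In one arm loss is random. In the other, the four highest on z = ρy + √(1 − ρ²)·noise are lost, where y is change and ρ its correlation with the propensity to leave. There were 40,000 simulated trials per row.

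| ρ | Bias (SD) | Type I error, nominal 5% |
|---|---|---|
| 0 | 0.00 | 5% |
| 0.3 | 0.12 | 6% |
| 0.5 | 0.20 | 8% |
| 1.0 (extreme) | 0.40 | 20% |

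At ρ = 1, the 12 retained from 16 have a mean about 0.40 SD from the full-arm mean. The bias scales with ρ: 0.3 × 0.40 = 0.12 and 0.5 × 0.40 = 0.20. For scale, the standard error with 12 per arm is √(2/12) = 0.41 SD.

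**4. Bias when the rule is the same in both arms.** With no true effect there is none. With a true effect of 1.0 SD it depends on the rule:

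- Common cut-off that loses 25% of the sham arm: 1.0 becomes 0.96, 0.90 and 0.68 at ρ = 0.3, 0.5 and 1.0.
- The worst 4 of 16 lost in each arm: 1.0 stays 1.00, because both means shift equally.

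**The case against.** The strongest reply is that the attendance wording only names the arms. The entries carry arm labels, and sections 1 and 2 use almost the same words for the schedule. The only exclusion actually stated is specific to a task, which suggests available-case analysis with everyone else kept. Arm membership also follows allocation, through a stimulation template made for each participant. The reminder about stopping may concern a single session rather than leaving the trial. All of this is plausible, and it rules out saying that the plan prescribes a completers-only analysis. It does not supply a population or a rule for missed visits.

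The cited study that the analysis is to follow may contain such rules. It cannot be seen here, so this stays open; a plan should in any case state them itself.

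A reader might infer three stronger things that the documents do not support:

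- **That one missed session removes a person from every analysis.** It would from an eight-session ANOVA, but not from a 2 x 2 ANOVA on sessions 1 and 8.
- **That identical loss in both arms always biases a true effect.** Step 4 shows that it depends on the rule.
- **That type I error is near 20%.** That needs correlation 1.0 and selection in one arm only, and nothing in the documents points to either.

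It is also fair to say that 32 people in an educational project do not justify elaborate modelling. The fix is therefore kept small.

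**Conclusion.** The omission is certain: no analysis set keeps all randomised participants, and no rule covers missed sessions or withdrawal. The lean towards completers is a fair reading rather than a stated rule. It rests on the attendance wording, the task-removal rule and the usual handling of incomplete cases in mixed ANOVA. It is firmest for G-SAS and CGT, two of the four primary outcomes.

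The size is illustrative only: 0 at no correlation, and 0.12 to 0.20 SD with type I error of 6% to 8% at correlation 0.3 to 0.5, given 4 of 16 lost per arm and outcome-related loss in one arm. The documents give no dropout rate or reasons, so the direction is unknown and the actual bias may be nil. This should be fixed before the data are analysed. It does not show that the trial's result would be wrong.

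**What to change.** 1. **Population.** Under Analysis sets/Subgroups, define the primary set as all randomised participants, analysed by allocated arm whatever number of sessions they attend. Keep eight-session attenders as a supportive set. Under Participants in section 2, say whether 16 per group means randomised or completing.
2. **Model.** For outcomes measured at all eight sessions, replace the mixed ANOVA and the task-removal rule with a likelihood-based mixed model on every recorded session. Include arm, session and arm-by-session, keep session 1 as a response so that people with only a baseline stay in, and use a simple covariance structure. State the contrast to be tested. Use the same model on sessions 1 and 8 for G-SAS and CGT, and note that it recovers little when only the baseline exists.
3. **Missing values.** Leave missed visits as missing. Limit item imputation to isolated items on multi-item questionnaires; it cannot apply to the single-line VAS.
4. **Sensitivity.** Add one simple analysis for missing week-8 values. For example, impute from the model within the allocated arm, add a shift, and report the shift at which the conclusion changes. With 4 of 16 missing, a shift of 1 SD moves that arm's mean by 4/16 = 0.25 SD.

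The cost is SAP wording and modest extra analysis work. The estimate will include people who attended fewer sessions and may be smaller than among completers, and the sensitivity analysis may show that the result is not robust.

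### As worded, one failed IST or SST run removes the participant from that task's whole analysis, discarding up to seven valid runs on a secondary outcome

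*Combined protocol and SAP*

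**What the plan says.** The SAP (section 5, Handling of missing values) expects few missing values, because the software does not let a participant move on without responding. For the computer tasks it allows one exception: "The only possible missing values would come by an error on the whole task, which will result in no data at all". The consequence follows directly: "In this case, we would withdraw this participant from the analysis of that specific task". The unit removed is the participant and the scope is the task's analysis; nothing limits the rule to the failed session. Imputation is described only for paper questionnaires.

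The schedule is given under Data source. There are measurements "at eight time points for VAS, PG-BOCS and secondary measures", which covers IST and SST. For the remaining two instruments, "Each participant will produce data at two time points for G-SAS and CGT measures". Section 2 (Trial procedures) agrees: CGT in sessions 1 and 8, IST and SST in every session. CGT and IST come before the stimulation/EEG protocol, and SST is done during stimulation.

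For the secondary measures, Statistical Procedures says: "Differences between sessions scores will be analysed with mixed between-within repeated measures ANOVA". The within-participant factor is time, and the independent variables list it as sessions 1 to 8. Both the secondary objectives and the analysis objectives include comparing each week's task performance with baseline.

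**The concern.** The rule sets the penalty per participant, while failures occur per run. With eight runs of a task there are eight chances to trigger it, and each time up to seven good runs go with the bad one. A rate that looks negligible per run need not be negligible per participant, and there are only 16 per arm.

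The loss also cuts against the plan's own aims. A week-versus-baseline comparison needs only session 1 and that week. If one follow-up run fails, baseline and six follow-up runs remain, so six usable comparisons are thrown away. The participant also drops out of the stimulation-by-time interaction, which the plan intends to use to look for cumulative effects.

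The point concerns failed runs in attended sessions. It does not concern missed visits or dropout.

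**Working it through.** **Inputs from the documents.** 16 per arm, so 2 × 16 = 32 participants. Runs per participant: k = 8 for IST and for SST, k = 2 for CGT. The plan gives no failure rate, alpha, power or effect size, so it has no figure of its own to reproduce here.

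**Direct count.** IST or SST: 8 − 1 = 7 valid runs discarded after a single failure. CGT: 2 − 1 = 1.

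**Scale, under assumptions.** Let p be the failure probability per run, assumed equal and independent across sessions. The values 1%, 2% and 5% are assumptions.

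- Share of participants removed = 1 − (1 − p)^k.
- Number removed = 32 × share.
- Valid runs discarded (k = 8; 32 × 8 = 256 runs in total) = 256 × (share − p).
- Standard error relative to complete data = 1/√(1 − share), if losses are similar in both arms.

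| | p = 1% | p = 2% | p = 5% |
|---|---|---|---|
| IST or SST: share removed | 1 − 0.99^8 = 7.7% | 1 − 0.98^8 = 14.9% | 1 − 0.95^8 = 33.7% |
| Participants removed, of 32 | 2.5 | 4.8 | 10.8 |
| Runs that failed, of 256 | 2.6 | 5.1 | 12.8 |
| Valid runs discarded, of 256 | 17.2 | 33.1 | 73.4 |
| SE relative to complete data | 1.04 | 1.08 | 1.23 |
| CGT: share removed | 1 − 0.99² = 2.0% | 1 − 0.98² = 4.0% | 1 − 0.95² = 9.8% |

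**What the fix would gain.** Complete data is not the right yardstick, because failed runs that cannot be repeated stay missing under the fix too. Take one week's change from baseline. The rule keeps a fraction (1 − p)^8 of participants. Using only participants with both runs observed keeps (1 − p)². The ratio of standard errors is therefore 1/√((1 − p)^6) = (1 − p)^−3, that is 1.03 / 1.06 / 1.17. A mixed model also uses participants with one of the two runs, so for such a comparison the gain lies roughly between these values and the 1.04 / 1.08 / 1.23 in the table.

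**Does the analysis model agree with the rule?** A repeated-measures ANOVA in its standard form needs a value at every level of time. A participant with one missing session is dropped whatever the missing-data paragraph says, so the rule and the model lead to the same loss.

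**The case against.** Four arguments carry weight.

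1. *The rule does not literally say that a failure in any one session triggers removal.* It could mean removal from one week's comparison with baseline, or only when a participant has no data on the task at all. Section 1 defines IST and SST change separately for weeks 2 to 8, which makes the first reading possible. The text states neither, however, and the ANOVA points the other way. An analyst following the words would delete the participant. What stands is that the wide reading is the plain one, not the only one.

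2. *The size is unknown.* This stands. The rates are assumed, and the plan expects few failures. If failures cluster in the same participants, fewer are lost at the same rate per run. A reader might infer from the 5% column that about a third of the sample will be lost; nothing in the documents supports that rate.

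3. *The primary outcomes are hardly touched.* This stands. A reader might infer that the rule damages the primary CGT analysis. But that endpoint is the change from session 1 to session 8, and if either run fails no change exists under any rule. PG-YBOCS, VAS and G-SAS are questionnaires, and the rule is written for failures of computer tasks.

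4. *A failed run may simply be repeated in practice.* The plan is silent on repeats, which is not a prohibition. But repeating is not free. Section 2 gives one hour for tasks and questionnaires. In sessions 1 and 8, CGT (10 minutes), IST (up to 15), EEG (5 + 5) and stimulation with SST (20) already add up to 55 minutes, before questionnaires and cap set-up.

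**Conclusion.** The point holds for IST and SST. On its plain wording, and in agreement with a complete-case repeated-measures ANOVA, the rule lets one failed run discard up to seven valid runs. The count follows from the schedule alone. The percentages rest on assumed, independent failure rates and show only how a small rate per run grows over eight sessions: at 1% per run, about 8% of participants leave the task's analysis.

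The loss falls on secondary outcomes. The documents do not support reading it as a threat to the primary analysis or as a forecast of heavy data loss. It is still worth correcting, because the data have already been collected, they serve a stated aim of the plan, and keeping them costs little.

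**What to change.** Make two changes in section 5, together:

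- **Handling of missing values:** state that when a run fails, only that session's value is missing and the participant's other sessions stay in the analysis.
- **Statistical Procedures:** analyse IST and SST with a linear mixed model for repeated measures on all observed sessions, with session 1 as one of the outcome time points. A participant whose session 1 run failed then still contributes later sessions. Week-versus-baseline contrasts and the stimulation-by-time interaction come from the same model.

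Rewording the rule alone would achieve nothing, since a complete-case ANOVA would still drop the participant.

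The cost is more than wording, because the analysis model for two secondary outcomes changes. The covariance structure should be fixed in advance: an unstructured matrix over eight sessions has 8 × 9 / 2 = 36 parameters, which is many for 32 participants. The model also assumes that failures are unrelated to the unobserved score, which is plausible for technical faults.

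Optional addition: allow one restart of a failed CGT or IST run before stimulation, where session time permits, and flag it in the data. This is the only measure that helps CGT. Its downsides are a possible overrun of the one-hour session and a slight practice effect.
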